## 4.2 Exclusion Criteria

1. Acute or rapidly enlarging dissection ( $>0.5$  cm increase over the preceding three months)
2. Prior descending thoracic aortic repair or endograft placement
3. Advanced renal or hepatic dysfunction
4. Poorly controlled diabetes requiring insulin
5. Active malignancy, pregnancy, or other metabolic or nutritional disorders that would contraindicate ketogenic therapy
6. Body mass index below  $18 \text{ kg/m}^2$
7. Inability to comply with dietary restrictions or follow-up imaging
8. Current enrollment in another interventional study, which in the opinion of the PI, may confound study results.
9. Patients who, in the opinion of the PI, are not suitable candidates for study participation.

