# 6.0 Study Interventions

## 6.1 Study Procedures

Participants will initiate a supervised ketogenic diet formulated to provide approximately 70-75% of calories from fat, 20% from protein, and less than 10% from carbohydrates, consistent with protocols successfully used in therapeutic epilepsy trials but adapted for adult cardiovascular patients. Caloric intake will be individualized to maintain stable weight and adequate micronutrient balance. Each participant will receive an orientation session with a registered dietitian, followed by weekly virtual or phone check-ins for the first month and bi-weekly thereafter. Educational materials, individualized meal plans, and recipes will be provided.

To ensure safety and adherence, participants will use a handheld ketone meter (Keto-Mojo) to measure  $\beta$ -hydroxybutyrate levels three times per week via saliva as well as finger-stick blood testing. These readings will be automatically uploaded to a secure, HIPAA-compliant cloud platform monitored by the study team. Serum ketone validation and metabolic panels, including electrolytes, lipid profiles, and liver function tests, will be obtained at baseline and every three months. A study coordinator will review adherence data weekly and contact participants who fall below target ketosis thresholds ( $\geq 0.5 \text{ mmol/L}$ ). Blood pressure logs and medication compliance will be reviewed at each visit to ensure consistent impulse control (see

Table 1).

Imaging assessments will be performed using standard-of-care CTA at baseline, 6, and 12 months. All studies will follow an institutional low-radiation surveillance protocol optimized for chronic dissection. Measurements will include maximal descending thoracic diameter, true and false lumen cross-sectional areas, and extent of thrombosis. Each scan will be reviewed by two blinded imaging readers to minimize measurement bias.

Participants will remain under the care of their treating cardiovascular physicians throughout the study, ensuring continuation of best-practice medical management. Any indication for surgical or endovascular intervention during the trial will be determined by the treating team using standard clinical criteria, and the patient will be considered to have reached the primary study endpoint.

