**Table 1: Schedule of Activities**

Assessment / Measurement	Baseline	Month 3	Month 6	Month 9	Month 12
Clinical Evaluation	✓	✓	✓	✓	✓
Dietitian / Coordinator Visit	Weekly (Month 0–1), then bi-weekly	✓	✓	✓	✓
Home $\beta$ -Hydroxybutyrate (Finger-Stick Meter)	Ongoing, $\geq 3\times$ per week	Continuous	Continuous	Continuous	Continuous
Serum $\beta$ -Hydroxybutyrate & Metabolic Panel	✓	✓	✓	✓	✓
Inflammatory Biomarkers (hs-CRP, IL-6, etc.)	✓	–	✓	–	✓
Fasting Lipids, HbA1c, Glucose	✓	–	✓	–	✓
Body Weight / BMI	✓	✓	✓	✓	✓
Blood Pressure & Pulse Logs	Continuous (weekly)	Continuous	Continuous	Continuous	Continuous
CT Angiography of Thoracic Aorta	✓	–	✓	–	✓
Adverse Event Review & Safety Labs	✓	✓	✓	✓	✓
Diet Adherence Assessment	✓	✓	✓	✓	✓

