## 9.0 Data Safety and Monitoring

The study Principal Investigator and Research Patient Coordinator will monitor for any safety concerns on an ongoing basis. Any symptomatic hypotension, electrolyte disturbance, or weight loss exceeding 10% of baseline will prompt protocol review and dietary adjustment by the study team. Should the principal investigator or designee become aware of any breach of confidentiality, or adverse event, the event will be reported according to institutional guidelines as outlined above, in Section 7.0

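### Exclusion 4 bars diabetes only when it is both poorly controlled and insulin-requiring, so a well-controlled insulin-treated patient is kept off the diet by judgement alone

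*Protocol*

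**What the plan says.** Protocol section 4.2 lists nine exclusions. The fourth is "Poorly controlled diabetes requiring insulin". It is the only criterion in sections 4.1 or 4.2 that mentions diabetes or insulin.

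Two other exclusions could reach a patient with diabetes. Exclusion 5 covers, besides malignancy and pregnancy, "other metabolic or nutritional disorders that would contraindicate ketogenic therapy". Exclusion 9 covers patients who, "in the opinion of the PI, are not suitable candidates for study participation".

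The diet in section 6.1 takes 70-75% of calories from fat, 20% from protein and "less than 10% from carbohydrates". Table 1 has a row for "Fasting Lipids, HbA1c, Glucose", ticked at baseline, month 6 and month 12. Section 9.0 names the events that lead to protocol review and dietary adjustment: "Any symptomatic hypotension, electrolyte disturbance, or weight loss exceeding 10% of baseline".

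**The concern.** The sponsor evidently regarded some diabetes on insulin as unsuitable for this diet, because it wrote a rule about it. As worded, the rule stops short of a group to which the same worry applies: patients on insulin whose control is good. A screener who works down the list finds one specific diabetes criterion, sees that the patient does not meet it, and may take the question as settled.

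What is at stake is safety, which is part of the primary objective in section 3.0. I assume, as general clinical reasoning and not from the protocol, that insulin dosing depends on carbohydrate intake, so that a sharp cut in carbohydrate calls for a plan for the insulin. The protocol contains no such plan.

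**Working it through.** No sample size, power or event figure is involved, so the check is a reading of the rule and of what stands behind it.

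**Step 1: what exclusion 4 covers.** Cross control (good or poor) with insulin (yes or no): 2 × 2 = 4 kinds of diabetes.

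| Control | Insulin | Barred by exclusion 4 as worded | Barred by an insulin clause alone | Barred by the full rewording |
|---|---|---|---|---|
| Poor | Yes | Yes | Yes | Yes |
| Good | Yes | No | Yes | Yes |
| Poor | No | No | No | Yes |
| Good | No | No | No | No |
| **Total barred** | | **1 of 4** | **2 of 4** | **3 of 4** |

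These totals count categories in the wording. They say nothing about how many patients fall in each. The row that matters here is the second.

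**Step 2: whether another criterion closes the gap.** The remaining inclusion and exclusion criteria do not name diabetes, insulin or glucose-lowering drugs. Exclusion 5 applies if the patient's diabetes is judged to contraindicate the diet, and exclusion 9 if the investigator judges the patient unsuitable. Both can keep a well-controlled insulin-treated patient out. Neither does so without a judgement about that patient.

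**Step 3: what the protocol provides if such a patient enters.**

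- Glycaemic tests by name: baseline, month 6 and month 12 (Table 1). A metabolic panel is also taken every three months. It may include glucose, but section 6.1 names only electrolytes, lipids and liver function among its contents.
- Action on a glucose value: none stated. The section 9.0 triggers are hypotension, electrolytes and weight.
- Insulin adjustment when the diet starts: none stated. The medication review in section 6.1 concerns blood pressure and impulse control.
- Risks listed in section 2.3: neither hypoglycaemia nor ketoacidosis is named.

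**Step 4: the result.** For a well-controlled insulin-treated patient, entry depends on discretion, and after entry there is no glucose or insulin rule specific to that patient.

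**The case against.** The strongest reply is that the matter is already handled. Exclusion 5 is as binding as any other exclusion. Diabetes is a metabolic disorder, and where it contraindicates the diet the patient is barred. Clinical judgement is needed to apply that, as it is for advanced renal or hepatic dysfunction in exclusion 3, and nobody calls that criterion defective. Exclusion 9 adds a further safeguard. After entry there are dietitian contacts (weekly, then bi-weekly), clinical and laboratory review every three months, and general safety monitoring by the investigator and coordinator under section 9.0. One could also read exclusion 4 as treating the need for insulin as the mark of poor control, so that all insulin users are meant.

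Much of this stands. It rules out saying that the protocol admits insulin-treated patients unprotected. It does not remove the point. Exclusion 5 is general, while exclusion 4 is specific and narrower. If the sponsor did mean all insulin users, the text should say so. If it meant to admit the well controlled, the missing insulin and glucose rules matter more.

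A reader might also infer an error from the home ketone readings. Section 6.1 introduces them with "To ensure safety and adherence, participants will use a handheld ketone meter", yet the only stated response is to "contact participants who fall below target ketosis thresholds", and section 9.0 has no trigger for high ketones. The documents do not support calling this a mistake. The 0.5 mmol/L value is a target for ketosis, reviewed as adherence data. The uploads are monitored by the study team, and safety oversight is described separately. Nothing in the text conflicts with the absence of an upper limit, and the documents supply no value for one.

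**Conclusion.** The point holds as a minor defect of wording. Exclusion 4 by rule bars only diabetes that is both poorly controlled and insulin-requiring. A well-controlled insulin-treated patient is kept off the diet only by judgement under exclusions 5 or 9, and there is no glucose trigger or insulin-adjustment rule should that judgement go the other way.

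This rests on the literal reading of exclusion 4 and on the stated assumption that insulin and carbohydrate intake have to be managed together. It does not rest on any rate of harm. The protocol gives neither the prevalence of diabetes among eligible patients nor an expected number of such entrants among the 15 participants, so neither can be put in figures. No endpoint, analysis or statistical result changes.

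It would be tempting to add that poorly controlled diabetes without insulin is equally a hole in the rule. The wording does leave that group out, but the documents give no reason why it needs barring, so the point does not depend on it.

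**What to change.** Reword exclusion 4 as *Any diabetes requiring insulin, or poorly controlled diabetes*. The insulin clause is the essential change: it replaces discretion with a rule for the group at issue. The second clause still depends on a view of what counts as poor control; the baseline HbA1c and glucose already in Table 1 can inform it. If the sponsor does not wish to bar poorly controlled diabetes without insulin, the insulin clause alone is enough.

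The cost is one amended line, with no new tests, visits or staff. The downside is possibly slightly fewer eligible patients in a small Marfan population, a number that the protocol does not allow to be estimated.

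Optionally, the study clinicians could set an upper action limit on the ketone readings already uploaded, with a high reading prompting clinical contact.

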## 4.3 Historical Control Cohort

Historical control data will be collected from previously published Marfan dissection cohorts, where approximately 20-25% of patients progress to intervention during the first year of follow-up.

# 6.0 Study Interventions

## 6.1 Study Procedures

Participants will initiate a supervised ketogenic diet formulated to provide approximately 70-75% of calories from fat, 20% from protein, and less than 10% from carbohydrates, consistent with protocols successfully used in therapeutic epilepsy trials but adapted for adult cardiovascular patients. Caloric intake will be individualized to maintain stable weight and adequate micronutrient balance. Each participant will receive an orientation session with a registered dietitian, followed by weekly virtual or phone check-ins for the first month and bi-weekly thereafter. Educational materials, individualized meal plans, and recipes will be provided.

To ensure safety and adherence, participants will use a handheld ketone meter (Keto-Mojo) to measure  $\beta$ -hydroxybutyrate levels three times per week via saliva as well as finger-stick blood testing. These readings will be automatically uploaded to a secure, HIPAA-compliant cloud platform monitored by the study team. Serum ketone validation and metabolic panels, including electrolytes, lipid profiles, and liver function tests, will be obtained at baseline and every three months. A study coordinator will review adherence data weekly and contact participants who fall below target ketosis thresholds ( $\geq 0.5 \text{ mmol/L}$ ). Blood pressure logs and medication compliance will be reviewed at each visit to ensure consistent impulse control (see

Table 1).

Imaging assessments will be performed using standard-of-care CTA at baseline, 6, and 12 months. All studies will follow an institutional low-radiation surveillance protocol optimized for chronic dissection. Measurements will include maximal descending thoracic diameter, true and false lumen cross-sectional areas, and extent of thrombosis. Each scan will be reviewed by two blinded imaging readers to minimize measurement bias.

Participants will remain under the care of their treating cardiovascular physicians throughout the study, ensuring continuation of best-practice medical management. Any indication for surgical or endovascular intervention during the trial will be determined by the treating team using standard clinical criteria, and the patient will be considered to have reached the primary study endpoint.

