## 1.0 Synopsis

Title:	Nutritional Ketosis as a Novel Therapeutic Strategy to Stabilize Chronic Aortic Dissection in Marfan Syndrome
Study Description:	Patients with Marfan syndrome who have chronic or residual aortic dissection remain at ongoing risk for progressive aortic dilation and eventual need for operative repair. Despite advances in antihypertensive therapy and open/endovascular/hybrid techniques, no medical therapy has been shown to slow aortic enlargement once chronic dissection is established. But promising results have been demonstrated in rodent studies utilizing ketogenic dietary interventions. Therefore, this prospective, single-arm, intent-to-treat pilot clinical trial will test the feasibility, safety, and potential efficacy of inducing and maintaining nutritional ketosis in patients with Marfan syndrome and chronic aortic dissection
Objectives:	
Primary Objective:
 
 
To test the feasibility, safety, and potential efficacy of inducing and maintaining nutritional ketosis in patients with Marfan syndrome and chronic aortic dissection (Prior type A dissection with residual distal dissection or Stanford Type B; and a maximal aortic diameter 4.0-5.0 cm).
 
 
Secondary Objective:
 
 
Observation of changes related to aortic dissection and inflammatory markers
 
Patient adherence to ketogenic dietary recommendations
 

Endpoints:	
Primary Endpoint:
 
 
Freedom from aortic intervention at 12 months compared with historical controls.
 
 
Secondary Endpoints:
 
 
Change in aortic diameter
 
Growth rate
 
Systemic inflammatory markers
 
Dietary adherence metrics
 

Study Population:	15 patients- Prospective Cohort 15 patients- Historical Control
Phase:	N/A
Description of Sites / Facilities Enrolling:	Washington University School of Medicine / Barnes-Jewish Hospital

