The main goal is to see how many patients can avoid needing aortic surgery within one year, compared with what is normally expected from past studies. We will also track how well patients follow the diet, how their aorta changes, and whether inflammation in their blood decreases.

[figure not shown]
If this approach proves safe and effective, it could become the first medical treatment aimed at stabilizing the aorta in Marfan syndrome, reducing the need for major operations and improving long-term health for people living with this genetic condition.

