### 3.0 Objectives and Endpoints

Objectives	Endpoints
Primary	
Test the feasibility, safety, and potential efficacy of inducing and maintaining nutritional ketosis in patients with Marfan syndrome and chronic aortic dissection	Freedom from aortic intervention at 12 months compared with historical controls.
Secondary	
Observation of changes related to aortic dissection and inflammatory markers  Patient adherence to ketogenic dietary recommendations  Explore the mechanistic relationship between circulating ketone levels, systemic inflammation, and aortic remodeling as measured by imaging and biomarker assays	Change in maximal descending thoracic aortic diameter and annualized growth rate Degree of false-lumen thrombosis Correlation between serum $\beta$ -hydroxybutyrate levels and aortic remodeling using finite-element imaging analysis Changes in systemic inflammatory and metabolic biomarkers Overall diet adherence and safety.

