### 4.0 Study Population

#### 4.1 Inclusion Criteria

1. Adults between 18 and 50 years old.
2. Ability to understand and willingness to sign an IRB approved written informed consent document.
3. Genetically or clinically confirmed Marfan syndrome

4. Chronic descending thoracic aortic dissection present for at least three months
5. Maximal descending thoracic aortic diameter must measure between 4.0 and 5.0 cm at baseline on contrast-enhanced CT angiography (CTA)
6. Have been clinically stable and consistent antihypertensive regimen for at least four weeks

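### Sections 6.1 and 6.2 count an indication for intervention as the primary event, while the endpoint and the historical rate are worded as interventions

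*Protocol*

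**What the plan says.** The protocol describes the primary event in several places.

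- **Synopsis and Section 3.0:** the primary endpoint is "Freedom from aortic intervention at 12 months compared with historical controls".
- **Section 4.3:** in the published cohorts, "approximately 20-25% of patients progress to intervention during the first year of follow-up".
- **Sections 6.1 and 6.2, in identical words:** "Any indication for surgical or endovascular intervention during the trial will be determined by the treating team using standard clinical criteria". The rest of that sentence gives the consequence for scoring: "and the patient will be considered to have reached the primary study endpoint".
- **Lay statement of the main goal, at the end of Section 2.1:** the aim is to see "how many patients can avoid needing aortic surgery within one year". This wording is based on need and mentions surgery only.

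Section 6.1 and Table 1 place the last CTA at month 12, and Section 6.2 ends active participation after 12 months.

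On eligibility, the Synopsis objective refers to "a maximal aortic diameter 4.0-5.0 cm" and names no segment for that diameter. Section 4.1 requires: "Maximal descending thoracic aortic diameter must measure between 4.0 and 5.0 cm at baseline".

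**The concern.** An indication and an intervention are different events. A patient may have an indication and not yet have had the procedure, or may never have it. Sections 6.1 and 6.2 make the indication sufficient; the Synopsis and Section 3.0 ask whether an aortic intervention took place. The historical figure is also described by intervention.

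An analyst who follows 6.1 may therefore set indications in the diet cohort against a benchmark described as interventions. An analyst who follows 3.0 would leave some of those participants event-free. The primary proportion then depends on which section is followed. The schedule makes this a practical matter, because the month-12 CTA can produce exactly the case on which the two rules disagree.

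**Working it through.** The protocol gives no calculation for the primary proportion, so there is no stated figure to reproduce. The check compares the rules on concrete cases and then sizes the difference.

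**Step 1. Cases under each rule**

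| Case | Sections 6.1/6.2 | Synopsis/Section 3.0 |
|---|---|---|
| Aortic repair performed by month 12 | Event | Event |
| Indication found at month 6, no repair by month 12 | Event | No event |
| Indication first found on the month-12 CTA, repair later | Event | No event |
| No indication, no repair | No event | No event |

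The second and third rows carry the disagreement.

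**Step 2. Weight of one participant**

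Inputs: 15 prospective participants (Synopsis); historical event rate 20-25% (Section 4.3), so implied freedom is 100 − 25 = 75% to 100 − 20 = 80%.

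- One participant: 1/15 = 6.7 points.
- Relative to the benchmark event rate: 6.7/25 = 27% to 6.7/20 = 33%.
- Events expected at the historical rate: 15 × 0.20 = 3.0 to 15 × 0.25 = 3.75.

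**Step 3. Illustration**

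Assume two participants have an indication but no procedure by month 12. This count is not in the protocol. Intervals are exact (Clopper-Pearson) 95%.

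- Counting performed interventions: 13/15 = 86.7% free (59.5 to 98.3), above 75-80%.
- Counting indications: (13 − 2)/15 = 11/15 = 73.3% free (44.9 to 92.2), below 75-80%.

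With one such participant the result is 12/15 = 80.0% (51.9 to 95.7), at the upper edge of the implied range.

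**Step 4. Range if the diet has no effect**

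Let p be the rate of performed interventions and f the number of indications without a procedure, as a fraction of procedures. The event rate under 6.1 is p × (1 + f), and apparent freedom falls by p × f. The protocol does not give f; 10% to 100% is an assumed range.

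| p | f | Rate under 6.1 | Expected events of 15 | Fall in apparent freedom |
|---|---|---|---|---|
| 20% | 10% | 22% | 3.3 | 2 points |
| 20% | 100% | 40% | 6.0 | 20 points |
| 25% | 10% | 27.5% | 4.1 | 2.5 points |
| 25% | 100% | 50% | 7.5 | 25 points |

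This is the gap that the definition alone would create if the published cohorts counted performed interventions only.

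**The case against.** **The need-based rule may be the intended one.** The lay goal speaks of needing surgery, and Section 2.3 gives the possible benefit as delaying the need for repair. Sections 6.1 and 6.2 could then be making the endpoint operational. That is fair, and 6.1 should not be assumed to be the slip. But the Synopsis and Section 3.0 still say something else, and the historical figure is not described in terms of need.

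**The result is too imprecise for this to matter.** The intervals in Step 3 overlap widely, and Section 10.0 sets numerical benchmarks only for retention and adherence. This stands: no formal decision flips. What changes is the side of the benchmark on which the estimate falls.

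**The 6.1 rule is the conservative one.** By definition alone it can only add events to the diet cohort. This also stands, and it bears on the fix.

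A reader might infer more than the protocol supports:

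- *That an indication for a non-aortic procedure would count.* Section 6.1 lacks the word aortic in that sentence, but the sentence refers to the primary endpoint, which is aortic, and it comes shortly after the CTA measurements. Context ties it to the aorta.
- *That the two cohorts are shown to be counted differently.* Section 4.3 does not say how the published cohorts defined or dated events. The rules may differ; that they do cannot be shown.
- *That events outside the descending aorta will add noise.* The protocol gives no frequency for them, and Section 4.1 can be read as refining the Synopsis.

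**Conclusion.** The contradiction is real and concerns the primary event itself. The protocol states two incompatible rules, so this is not detail left to an analysis plan: a plan could follow one section only by overriding another.

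The firm part of its size is 6.7 points per affected participant, where only 3.0 to 3.75 events are expected. The move from 86.7% to 73.3% rests on an assumed two participants, and the 2 to 25 point range rests on the assumed f and on published cohorts that counted performed interventions. Neither is a forecast. That a repair prompted by the month-12 CTA falls outside the window is a practical expectation and not a logical necessity.

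The segment wording is a lesser inconsistency. For example, a descending diameter of 4.3 cm with a root of 5.3 cm meets Section 4.1 but, on a literal reading, fails the Synopsis. The two places must be reconciled; which of them is right is not judged here.

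**What to change.** 1. Use one event definition in the Synopsis, the lay goal in Section 2.1, and Sections 3.0, 6.1 and 6.2.
2. For the historical comparison, count aortic interventions performed within 12 months, matched to whatever the chosen published cohorts count, and state in Section 4.3 what that is.
3. Report indications without a performed intervention, including those from the month-12 CTA, as a separate line or sensitivity analysis.
4. Reconcile the diameter wording in the Synopsis with Section 4.1 so that one segment is named.

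Do not narrow the primary event to one aortic segment, or add rupture and aortic death to it, unless the control cohorts report events that way. The figure in Section 4.3 is described only as intervention, so either step would open a new mismatch.

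The cost is protocol wording and one extra reported line; clinical care is unchanged. The drawback is that fewer events count in the primary than under 6.1, so apparent freedom in the diet cohort can only stay the same or rise. The indication-based result must therefore be shown beside the primary one.
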